12.4 Data and Safety Monitoring

The Data and Safety Monitoring (DSM) Plans at Memorial Sloan Kettering Cancer Center were approved by the National Cancer Institute in September 2001. The plans address the new

policies set forth by the NCI in the document entitled “Policy of the National Cancer Institute for Data and Safety Monitoring of Clinical Trials” which can be found at:

<http://www.cancer.gov/clinicaltrials/conducting/dsm-guidelines/page1>. The DSM Plans at MSK were established and are monitored by the Office of Clinical Research. The MSK Data and Safety Monitoring Plans can be found on the MSK Intranet at:

<http://inside2/clinresearch/Documents/MSKCC%20Data%20and%20Safety%20Monitoring%20Plans.pdf>

There are several different mechanisms by which clinical trials are monitored for data, safety and quality. There are institutional processes in place for quality assurance (e.g., protocol monitoring, compliance and data verification audits, therapeutic response, and staff education on clinical research QA) and departmental procedures for quality control, plus there are two institutional committees that are responsible for monitoring the activities of our clinical trials programs. The committees: *Data and Safety Monitoring Committee (DSMC)* for Phase I and II clinical trials, and the *Data and Safety Monitoring Board (DSMB)* for Phase III clinical trials, report to the Center’s Research Council and Institutional Review Board.

During the protocol development and review process, each protocol will be assessed for its level of risk and degree of monitoring required. Every type of protocol (e.g., NIH sponsored, in-house sponsored, industrial sponsored, NCI cooperative group, etc.) will be addressed and the monitoring procedures will be established at the time of protocol activation.

13 STATISTICAL CONSIDERATIONS

13.1 Study Design/Endpoints

The prognosis for patients with metastatic disease is poor, but this is an encouraging time and there are many agents which could be examined. Therefore, 2 investigational treatment strategies will be assessed in this trial.

A total of 80 patients with advanced stage melanoma will be randomized to either trametinib plus GSK2141795 or trametinib alone (40 evaluable patients per arm). The primary endpoint of this study is time to progression (PFS) defined from the date of randomization to the date of documented progression or death. Patients will be assessed for progression every 8 weeks. PFS will be calculated as time from randomization to the earlier date of objective disease progression per RECIST criteria or death due to any cause in the absence of progression; patients who have not progressed or died at the time of analysis will be censored at the time of their latest evaluable objective tumor assessment. It is estimated that median PFS for the trametinib arm is 16 weeks based upon the results of CTEP8443 as presented at the 2013 ASCO Annual Meeting which demonstrated a median PFS of 15.9 weeks with selumetinib (n = 47, 95% CI, 8.4 – 23.1 weeks). With 80 patients and with 76 progression events, the probability is 80% that the study will detect a treatment difference at a one-sided 5% significance level, if the true hazard ratio is 0.56.

Overall survival will be analyzed using the same methods as used for PSF. Overall survival will be calculated as time from randomization to death due to any cause; patients who have not died at the time of analysis will be censored based on the last recorded date on which the subject was known to be alive.

This is based on the assumption that the accrual period will be approximately 26 months, the follow up period will be 12 months, and the median PFS for trametinib alone is 16 weeks. It is anticipated that 3 patients per month will be accrued to this study and hence the study accrual will be completed in approximately two years and the trial will be completed in approximately three years.

An early stopping rule for futility will be applied. Clinical benefit rate will be examined in each arm after 40 evaluable patients have been accrued (20 patients per arm). As noted above, early analysis of our on-going trial of selumetinib versus temozolomide in patients with advanced uveal melanoma, 40% of patients treated with selumetinib achieved disease control beyond 16 weeks. If at least two patients have achieved a radiographic response as defined as a RECIST partial or complete response in each arm, then the trial will continue as planned. If zero or one patient achieves a RECIST response among the 20 patients of an arm, then that arm will be terminated. The upper bound of the 95% confidence interval for no clinical benefit out of 20 patients with this early stopping rule is 25%. PFS will also be reviewed at the end of the first stage, and adjustment to the futility rule may be considered if significant PFS prolongation is obtained in the absence of sufficient numbers of RECIST responses. If we stop one arm of the trial due to futility, then we may revert to a single arm phase II study. The alternate arm may continue to accrue 40 patients. The plan for the second stage will be finalized after discussion with the sponsor. At the end of the study we will estimate the progression free survival distribution for that arm and provide the median PFS along with a 95% confidence interval.

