13.2 Sample Size/Accrual Rate

This study design requires the accrual of up to 60 patients with advanced uveal melanoma.

This study will be a multi-institution phase II study led by MSK. The Melanoma Service at MSK sees between 2 and 4 patients with uveal melanoma monthly, with 75% or more presenting with metastatic disease. We anticipate accrual of 2 patients monthly from MSK alone. Once the study is open at all participating centers, we conservatively estimate an accrual of 3 patients per month.

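### 80 patients, 76 events and 80% power still stand for the A v B comparison, although 13.2 limits accrual to 60 and Arm B is closed; no post-closure reading built on the plan's own numbers gives 80%

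*Combined protocol and SAP*

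**What the plan says.** Section 13.1 sets up a two-arm comparison: "A total of 80 patients with advanced stage melanoma will be randomized", 40 evaluable per arm. It then gives the power statement: "With 80 patients and with 76 progression events, the probability is 80% that the study will detect a treatment difference", at a one-sided 5% level and a true hazard ratio of 0.56. The Schema also gives 80 patients randomised 1:1, and the accrual table in 3.4 totals 40 + 40 = 80. The timeline in 13.1 assumes that "the accrual period will be approximately 26 months" and says "It is anticipated that 3 patients per month will be accrued to this study".

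Section 13.2 gives a different total: "This study design requires the accrual of up to 60 patients with advanced uveal melanoma".

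The Schema and sections 4.4, 4.5 and 5.1 record that Arm B met its futility rule as of 11/06/2015 and that remaining patients go to Arm A only. Section 1.1 still gives the comparison of PFS between the two regimens as the only primary objective.

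For a stopped arm, 13.1 commits to one analysis of the continuing arm: "we will estimate the progression free survival distribution for that arm and provide the median PFS along with a 95% confidence interval". The rest is open: the trial may revert to a single-arm study, "The alternate arm may continue to accrue 40 patients", and "The plan for the second stage will be finalized after discussion with the sponsor". The documents do not record the finalised plan. Section 13.6.2 bases the main PFS analysis on patients who were randomised and received at least one dose.

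**The concern.** Two totals stand in current text for the same primary analysis, and the stated events and power belong to only one of them. Each patient contributes at most one first PFS event, so a 60-patient trial cannot produce 76. Closing Arm B also ends randomised allocation between the arms: anyone entered later receives trametinib alone and has no concurrent Arm B counterpart.

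Three things therefore remain unclear. The first is how many patients Arm A is meant to hold. The second is whether A v B is still a one-sided 5% test with a power claim. The third is whether Arm A patients entered after closure belong in that comparison; 13.6.2 does not deal with them. A reader who took 13.1 at face value would credit the A v B result with more power than the remaining design can supply.

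**Working it through.** **Inputs.** From 13.1: hazard ratio 0.56, one-sided alpha 0.05 (z = 1.645), 80 patients at 1:1, 76 events, accrual of 26 months at 3 a month, and a planned futility look at 20 per arm with the other arm possibly continuing to 40. From 13.2: at most 60 patients. The numbers per arm when Arm B closed are not given, so every split below is an assumption.

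**Step 1. Reproduce the plan's figure.** Schoenfeld power = Φ(√(d·p·(1−p))·|ln 0.56| − 1.645), where d is events, p is the share of patients in one arm, and |ln 0.56| = 0.580.
- d = 76, p = 0.5: √19 × 0.580 = 2.527; 2.527 − 1.645 = 0.882; power 81.1%.
- Freedman: √76 × (1 − 0.56)/(1 + 0.56) = 2.459; 2.459 − 1.645 = 0.814; power 79.2%.

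The stated 80% lies between the two, so the calculation is sound for the design it describes.

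**Step 2. Which total does the timeline fit?** 26 × 3 = 78, close to 80. Section 13.1 also says about two years: 24 × 3 = 72. At 3 a month, 60 patients need 60/3 = 20 months. Both stated durations are longer than that, so the timeline was not written for 60.

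**Step 3. Events under the limit of 60.** The maximum is 60. At the plan's own event share, 76/80 = 95%, it is 0.95 × 60 = 57. For 40 patients the corresponding range is 38 to 40.

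**Step 4. Power after closure (same formula).**

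| Reading | Events | p | Power |
|---|---|---|---|
| 60 patients, 30 v 30, every patient with an event (ceiling) | 60 | 1/2 | 72.6% |
| 60 patients, 40 in Arm A v 20 in Arm B | 57 to 60 | 1/3 | 66.2 to 68.2% |
| Concurrently randomised only, 20 v 20 | 38 to 40 | 1/2 | 55.7 to 57.5% |
| 80 patients, 60 in Arm A v 20 in Arm B | 76 | 1/4 | 70.7% |

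Freedman at 1:1 gives 70.5% at 60 events and 55.5% at 40 events, so the picture does not depend on the approximation.

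**Step 5. What would 80% require?** d·p·(1−p) must reach ((1.645 + 0.842)/0.580)² = 18.4. With 60 events the largest possible value is 60/4 = 15, so the 60 limit rules out 80% at any split. With 80 patients and 76 events, p(1−p) must be at least 18.4/76 = 0.242, so p is at least 0.41. That means about 33 patients in Arm B, well above the 20 at which the futility look was planned.

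**The case against.** The strongest reply is that 13.1 foresaw this situation. It provides for stopping an arm, continuing the other to 40, and reporting that arm's median PFS with a 95% CI. On that view 60 is simply 20 + 40, and the 80-patient text is left over from before the stop. Much of this stands. The plan is not silent, and the single-arm estimate is a commitment. But no text says where 60 comes from. The words on Arm A's size can mean 40 in total or 40 more, and they are permissive. The stop has been written into the protocol without the finalised second-stage plan.

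Three stronger readings are tempting, and the documents do not support them:
- A reader might infer that closing Arm B alone makes 76 events impossible. It does not. With 80 patients split 60 v 20, 76 events could occur. The impossibility comes from the 60 limit.
- A reader might infer that the power calculation is wrong. It reproduces.
- A reader might infer that the analyst is left to choose the analysis late. Section 13.1 assigns the second-stage plan to discussion with the sponsor; what is missing is the outcome of that discussion.

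It is also fair to say that power for a comparison whose experimental arm has stopped for futility has little practical use. That argues for withdrawing the power claim, not for leaving it in place.

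**Conclusion.** The point holds as an internal inconsistency that needs correcting. The Schema, 3.4 and 13.1 plan for 80 patients, 13.2 allows 60, and the 76-event, 80%-power statement describes a design that ended when Arm B closed.

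Under the 60 limit the ceiling is 72.6% whatever the split, and that conclusion needs no assumption about arm sizes. The other figures do. The 40 v 20 and 20 v 20 results take Arm B to hold 20 patients, the number at the planned look. So does the 70.7% for 60 v 20, which in addition uses Arm A patients with no concurrent Arm B counterpart. If the actual Arm B number was larger, the figures for an 80-patient total would rise. The match between 60 and 20 + 40 is plausible but unconfirmed.

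**What to change.** 1. State one total and one Arm A target in the Schema, 3.4, 13.1 and 13.2. If 60 is meant as 20 + 40, the sponsor should confirm it and say so.
2. Label the 80-patient, 76-event, 80%-power statement as the original design, which no longer applies.
3. In 1.1 and 13.1, declare A v B descriptive after the futility stop: report the hazard ratio with a confidence interval and make no power claim. For scale, with 40 events at 1:1 the 95% limits are the estimate divided and multiplied by exp(1.96 × √(4/40)) = 1.86.
4. In 13.6.2, limit A v B to patients randomised before Arm B closed. Later Arm A patients contribute only to the Arm A estimate.
5. Keep the Arm A median PFS with its 95% CI as the estimate for the continuing arm.

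For consistency, the comparative objectives in 1.2 and the 1:1 text in 5.1 and 13.3 should carry the same note. The cost is a wording amendment, with no new patients or data. The downside is that the stated power becomes less favourable or is withdrawn.

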1.2 Secondary Objectives

- To compare overall survival between those treated with trametinib alone and those treated with the combination of trametinib and GSK2141795
- To compare the overall response rate between those treated with trametinib alone and those treated with the combination of trametinib and GSK2141795
- To compare the safety and toxicity between those treated with trametinib alone and those treated with the combination of trametinib and GSK2141795

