4.4 Randomization

All patients will be randomized to trametinib alone or in combination with GSK2141795. After eligibility is established and immediately after consent is obtained, patients will be registered in the Protocol Participant Registration (PPR) system and randomized using the Clinical Research Database (CRDB), between the hours of 8:30am and 5:30pm (ET), Monday - Friday. Randomization will be accomplished by the method of random permuted block, and patients will be stratified by (i) the presence or absence of liver involvement and (ii) LDH (< 2 times ULN versus two times above (≥ 2 x) the upper limit of normal) (see [section 5.1](#)).

As of 11/06/2015, Arm B met the specified stopping rule for futility. The remaining patients will be accrued to Arm A, no patients will be enrolled to Arm B or Crossover therapy.

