13.4 Analysis of Secondary Endpoints

Analysis of secondary endpoints will be exploratory and hypothesis-generating.

Progression-free survival and overall survival curves will be generated using Kaplan-Meier methodology. Toxicity across both arms will be reported by type, frequency and severity according to the NCI Common Toxicity Criteria. Response rate (CR+PR) by arm will be calculated along with a

95% confidence interval.

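### Arm B was closed on its response count, so the unadjusted A v B response difference that the plan still lists is expected to favour Arm A even if the regimens are equal

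*Combined protocol and SAP*

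**What the plan says.** Section 13.1 sets one look when 20 evaluable patients per arm have been accrued. The trial goes on as planned on this condition: "If at least two patients have achieved a radiographic response as defined as a RECIST partial or complete response in each arm". Otherwise, "If zero or one patient achieves a RECIST response among the 20 patients of an arm, then that arm will be terminated". There is some discretion: "adjustment to the futility rule may be considered if significant PFS prolongation is obtained". If one arm stops, the study may become single-arm, and "The alternate arm may continue to accrue 40 patients". Section 13.2 gives a total of up to 60, which matches 20 + 40.

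The schema and sections 4.4, 4.5 and 5.1 record the outcome: "As of 11/06/2015, Arm B met the specified stopping rule for futility". All remaining patients go to Arm A.

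The response objective in 1.2 is unchanged: "To compare the overall response rate between those treated with trametinib alone and those treated with the combination of trametinib and GSK2141795". Section 13.4 says "Response rate (CR+PR) by arm will be calculated" with a 95% confidence interval, and calls secondary analyses exploratory. No section adjusts the response estimates for the stopping rule, mentions the selection, or withdraws the comparison now that Arm B is closed.

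**The concern.** The quantity that decided which arm closed is the same quantity that is later estimated by arm and compared. If Arm B closed under the rule, its first-stage rate is at most 1/20 (5%) whatever its true rate. If Arm A passed, its first-stage rate is at least 2/20 (10%). Raw rates set side by side therefore carry a selection effect as well as any treatment effect.

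Two uses are at stake. A reader may take the raw difference as evidence against adding GSK2141795. A later trial may plan on Arm A's all-patient rate. The usual remedy for non-concurrent patients, restricting to the first 20 per arm, does not help here, because those are the patients on whom the selection was made.

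**Working it through.** **The plan's own figure.** Section 13.1 attaches an upper 95% bound of 25% to the rule. The exact (Clopper-Pearson) two-sided upper limit is 24.9% for 1/20 and 16.8% for 0/20. The 25% therefore reproduces at the stopping boundary of 1 in 20.

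**Inputs.** From 13.1: 20 per arm at the look, stop on 0-1 responses, continue on 2 or more, final size 40 for the continuing arm. The true response rate p is an assumption. The documents offer anchors of 0/16 (phase I trametinib in uveal melanoma, section 2.2.1.2) and 7/46 = 15% (selumetinib, section 2.3.3). I use 5, 10 and 15%, the same in both arms.

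**Formulas.** Let X be Binomial(20, p) and q = 1 - p.

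- P(stop) = q^20 + 20·p·q^19 = q^19·(1 + 19p)
- Arm B, given stopping: E[X/20 | X ≤ 1] = p/(1 + 19p)
- Arm A first stage, given passing: E[X/20 | X ≥ 2] = p·(1 - q^19)/(1 - P(stop))
- Arm A over 40: the mean of that figure and p, since the second 20 are unselected

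**Worked case, p = 10%.** q^19 = 0.1351 and P(stop) = 0.3917. Arm B = 0.10/2.9 = 3.45%. Arm A first stage = 0.10 × 0.8649/0.6083 = 14.22%. Arm A over 40 = (14.22 + 10)/2 = 12.11%. Gap = 12.11 - 3.45 = 8.7 points.

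| True rate, both arms | P(stop) | Arm B (20) | Arm A (40) | Gap, points | Bias B | Bias A | Gap, first 20 v 20 | P(B stops, A passes) |
|---|---|---|---|---|---|---|---|---|
| 5% | 0.736 | 2.6% | 8.4% | 5.8 | -2.4 | +3.4 | 9.2 | 19% |
| 10% | 0.392 | 3.45% | 12.1% | 8.7 | -6.6 | +2.1 | 10.8 | 24% |
| 15% | 0.176 | 3.9% | 16.2% | 12.3 | -11.1 | +1.2 | 13.5 | 14% |

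Outside this range the gap is 5.1 points at 3% and 16.4 at 20%. Arm B's bias is the larger part at 10 and 15%. At 5% Arm A's is larger (3.4 of 5.8).

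**Arms that truly differ.** With A at 15% and B at 5%, the expected raw gap is 16.2 - 2.6 = 13.6 points against a true 10, so selection adds 3.6. This pattern of outcomes then has probability 0.736 × 0.824 = 61%. With A at 10% and B at 3%, the expected gap is 12.1 - 1.9 = 10.2 against a true 7, so selection adds 3.2.

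**If Arm A did not pass on responses.** If Arm A's continuation carried no information about its count, the gap is Arm B's bias alone: 2.4, 6.6 or 11.1 points. If Arm A was kept on PFS despite 0-1 responses, its expected rate over 40 is the mean of p and Arm B's figure. The gap is then half of Arm B's bias: 1.2, 3.3 or 5.6 points.

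**The case against.** The strongest reply is symmetry. Before the look the rule treats both arms alike, so at equal rates the expected difference is zero and one arm's raw final rate is biased by only about -1 point. That is correct, and it rules out saying that the design favours Arm A as such. It does not settle the matter, because the outcome of the look is now written into the protocol and any reported difference is conditional on it.

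A reader might also infer that most of an observed A v B difference would be an artefact. The documents do not support that. It follows only if the arms are equal, in which case this outcome occurs in 14 to 24% of trials at the three rates. When the arms differ, the selection share falls, as shown above.

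The planned output is modest. Section 13.4 gives rates with intervals, names no test and no difference estimate, and is labelled exploratory. The intervals hold up: given continuation, Arm A's exact 95% interval covers in 95.2 to 98.5% of cases at the three rates. Arm B's possible intervals (0 to 16.8% for 0/20, 0.1 to 24.9% for 1/20) contain all three. A two-sided Fisher test of 20 v 40, given this outcome, would reject in 0.1, 2.3 and 9.3% of trials at 5, 10 and 15%, so inflation appears only at the top of the range and for a test that is not planned. Arm A's bias is at most about one standard error (3.4, 4.7 and 5.6 points for n = 40). All of this lowers the severity. None of it corrects the point estimates or the word compare in 1.2.

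Finally, Arm A's interim count is not given, the PFS provision is discretionary, and no accrual pause is stated. Over-running or later responses in Arm B would shrink the gap.

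**Conclusion.** The point stands as a conditional one. With Arm B closed under the rule, and with Arm A assumed to have passed and to reach 40, the raw response difference is expected to favour Arm A by about 6, 9 or 12 points at equal true rates of 5, 10 or 15%. These are expectations and not minimums: 1/20 v 2/40 gives no difference at all.

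Two further inferences should be resisted. Arm A's all-patient rate is not unusable, since its bias is +3.4 to +1.2 points. Nor is a PFS comparison in concurrently randomised patients a clean substitute: a responder is by definition not progressing at that time, so selection on response can carry into first-stage PFS. I have not sized that effect. Severity is low to moderate.

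**What to change.** - **Section 1.2:** change the response objective from a between-arm comparison to estimation within each arm.
- **Section 13.4:** state that response rates are conditional on a response-based stopping rule, and that no A v B response difference will be interpreted as a treatment effect.
- **Arm A:** beside the all-patient rate, report either the rate in patients enrolled after the look or a two-stage estimate adjusted for the rule.
- **Arm B:** report the observed count with an exact 95% interval, labelled as biased downward by the stopping rule. Giving the count does not remove the bias, so the label is needed.
- **PFS:** note that first-stage comparisons may carry some of the same selection.

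The cost is wording and one extra estimate, with no change to treatment, visits or data collection. The post-look estimate is less precise: at a 10% rate its standard error is √(0.10 × 0.90/20) = 6.7 points, against √(0.10 × 0.90/40) = 4.7 for all 40.

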13.2 Sample Size/Accrual Rate

This study design requires the accrual of up to 60 patients with advanced uveal melanoma.

This study will be a multi-institution phase II study led by MSK. The Melanoma Service at MSK sees between 2 and 4 patients with uveal melanoma monthly, with 75% or more presenting with metastatic disease. We anticipate accrual of 2 patients monthly from MSK alone. Once the study is open at all participating centers, we conservatively estimate an accrual of 3 patients per month.

